Central to the project is the efficacy trial, which is the second stage in a research series towards a better education of doctors in psychiatry. The RCT follows an initial quantitative pilot study that had promising results and a qualitative study of the use of the video library during the clinic stay. As such, the project follows the Tryg Foundation's research strategy towards implementing new procedures. In terms of subject matter, the project involves two categories: Within "Mental Health", it is especially in the project's focus on improving measurements among front staff, ie doctors. Within the "Patient First", it is especially within the effective training of practitioners. At the same time, the project has initiated the use of authentic patients in learning videos, within one of the most stigmatized medical

disciplines. The patients support it and want to contribute. It can therefore serve as a paradigmatic example of training front staff with this kind of patient involvement.

Project Aims

- To examine the effect of having an e-course on mental status exam including a video library consisting of authentic patient videos available during the ordinary teaching course, on the competencies within the description of mental status exam compared to simply having an e-course on mental status exam available during clinical psychiatry in 10th semeste

Project Content and Activities

- To improve the potential of the video e-library as self-study learning material through 1) extension with audio recordings of the clinical reasoning behind the MSE upshots; 2) additional video recordings; 3) self-study tasks; 5) a compendium of MSE phenomena to apply when solving the tasks.
- To investigate the level of MSE skills among trainee doctors and specialists, and explore what are the most difficult dimensions of the MSE.
- To carry out the RCT across three terms, testing all students at end of their rotation with the MSE skills test, and collecting pre and post survey data.
- Analyzing data and writing up at least three international peer-reviewed papers.
- Oral dissemination of project results at national and international meetings and conferences.
- Presenting the project at our research webpage in Danish and English

Succes criteria and milestones

| Goals | Success Criteria | Data & Documentation | Prerequisites |
|---|--|---|---|

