The main study is a two-armed, pragmatic cluster-randomised, superiority, partial-blinded, randomized controlled trial where the experimental intervention is in addition to the clinic stay, one group get access to the videotape and e-course on mental status exam (V), are compared with students in another group who only get the e-course on mental status exam (N-V). Primary outcome is score on the MSE skills test, after the clinical rotation. See figure 1 of the clinical course in psychiatry, illustrating the difference between conditions. Data management and randomization is computerized, the only stratification is by location (hospital). Allocation into two equal size arms, will

Add-on e-learning in psychiatry: Effect on MSE skills

be in variable blocks of 4, 6, and 8. See figure 2, for draft CONSORT diagram. A preparatory phase before onset of the RCT includes improvements in the content of the video e-library, see timeline in figure 3. Sub-study 1 is a cross-sectional investigation, entailing the collection of MSE skills scores and survey data among attendees at the annual meeting of the Danish Psychiatric Society (DPS). Trial protocol and Statistical Analysis Plan will be published at ClinicalTrials.gov.

RCT Feasibility

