The faculty office allocates the 5th year (4th term master) students, in three shifts per term, to 12 different locations (different departments or different locations within departments i.e. Mental Health Centre Copenhagen has students placed at Rigshospitalet, Gentofte, Bispebjerg and Frederiksberg). Group size at each location/shift varies between 2-14 (fewer in peripheral locations). Each term approximately 240 5th year students are allocated to the clinical course in psychiatry, which is mandatory. Our preliminary study had nearly 100 % recruitment success, but it was not a RCT. At the MSE skills test, we had drop-out ranging from 20-26%, with the largest drop-out when the skills test were conducted at Panum, in opposition to testing at the local hospital. However, now the MSE skills test will be carried out as a Zoom© webinar with adjoining questionnaire in SurveyXact, and scheduled in the late afternoon, probably lowering the drop-out rate. Sample size calculation based on our preliminary study, setting a meaningful difference to 1.25 point on the MSE skills test, yields a group size of 88, i.e. a total of 176 students. Given some expected drop-out, we will recruit at least 220 students, and the study will need to be carried out at least across three terms. Incitement for full participation is the possibility of access to the video library for all participating students the week before the exam in clinical psychiatry.

Participants

Maximum 500 5th year medical student at the University of Copenhagen in 2022

Inclusion criterion: Consent

Exclusion criterion: Previous participation in teams with videotek access.

Substudy 1: Approximately 100 doctors attending DPS annual meeting March 2021. Previously tested doctors (2017) will be excluded. Alternatively, this could also be conducted as a webinar based test.

Procedures

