Information about the study will be given in emails send at term start to all 4th term students (i.e. in August and January) in Absalon (UCPH student/teacher communication portal). The week prior to the course in psychiatry, the shift (Hold) of students, i.e. 60-70 students, will receive another information email, and they will be asked for consent by email, particularly for those not planning to attend the lectures in the first week. Oral information about the study will be given after lectures Monday and Tuesday in the lecture week, and electronic signed consent on paper will be gathered by SurveyXact. Consenting students will be entered in the data management system, and randomized by the end of the lecture week. The first day of the clinical rotation participating students will be informed of their allocation, whether they have access to the video e-library or not. All participating students will be

Add-on e-learning in psychiatry: Effect on MSE skills

tested with the MSE skills test in webinars either Mondays, Tuesdays or Wednesdays after the clinical rotation. Questionnaires will be sent by Survey Exact at start and end of the clinical rotation. All students participating in the MSE skills test will be given access to the video e-library the week before the oral exam in clinical psychiatry.

Partial blinding

As mentioned, it will not be possible to blind students or local lecturers to allocation group. An unblinded secretary draws the allocation list, sends emails informing the students of allocation, and gives them access to the video e-library on Absalon. The blinded research assistant will carry out the MSE skills testing, they and the assisting statistician will be blinded to student allocation until a conclusion is drawn based on concealed group allocation.

Experimental Add-on Intervention – Video-based self-regulated training

The intervention consists of access to the video e-library on Absalon. Consenting to participate the students also consent to see at least 12 videos, in pre-arranged order. At the end of the clinical attachment they will fill out a survey asking for the time spent at each task/video, and for their evaluation of the e-library. But data on the use of the video-library will also be extracted from Absalon data reports.

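### Does limiting the trial to 2022 while asking for three terms put the recruitment target of 220 at risk?

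*Protocol*

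**What the plan says.** Four places in the protocol bear on how long recruitment lasts and how many students it yields.

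- **RCT Feasibility** gives the sample size for a difference of 1.25 points on the MSE skills test: it "yields a group size of 88, i.e. a total of 176 students". It then allows for drop-out: "we will recruit at least 220 students, and the study will need to be carried out at least across three terms". The supply is also stated there: "Each term approximately 240 5th year students are allocated to the clinical course in psychiatry". On uptake it says: "Our preliminary study had nearly 100 % recruitment success, but it was not a RCT".
- **Project Content and Activities** repeats the term count: "To carry out the RCT across three terms, testing all students at end of their rotation".
- **Participants** describes the population as "Maximum 500 5th year medical student at the University of Copenhagen in 2022". The criteria that follow are consent (inclusion) and earlier membership of a team with access to the video library (exclusion).
- **Procedures** says that information emails go out "at term start to all 4th term students (i.e. in August and January", which places two term starts in each calendar year, and puts a shift at 60 to 70 students.

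The Design section refers the reader to a schedule, "see timeline in figure 3", which is not reproduced in the text at hand.

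**The concern.** Three terms cannot all start in 2022. If the feasibility sentence means that 220 students cannot be had in fewer than three terms, then holding to 2022 means missing 220. If the third term goes ahead, its students lie outside the year named under Participants; with equal terms they would be 240 of 720, one third of those approached. The version at hand is dated 28 February 2023, after a January 2023 term start, and its text does not say whether that term counts.

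The possible stakes are power and eligibility. Should two terms bring in only two thirds of 220, fewer than the required 176 students would be tested, and a true difference of 1.25 points would be missed more often. Should the third term be used, a reader could ask whether a third of the sample met the written description of the population.

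**Working it through.** **Inputs.** From RCT Feasibility: 176 tested students needed, floor of 220 recruited, about 240 students per term, three shifts per term, earlier drop-out of 20% to 26% at the skills test. From Procedures: 60 to 70 students per shift, two term starts per year. From Participants: ceiling of 500, year 2022. From the table of success criteria and milestones: data from 460 students.

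**Step 1: reproduce the floor.** Recruits = tested/(1 − drop-out) = 176/(1 − 0.20) = 220, an exact match at the lower end of the earlier drop-out. At 26% it would be 176/0.74 = 237.8, so 238. The 88 per group cannot be rebuilt, because the SD, alpha and power are not given in the protocol; nothing below depends on them except where stated.

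**Step 2: consent needed.** Students available = terms × students per term. The stated intake is 240 per term; three shifts of 60 to 70 give 180 to 210. Both are used.

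| Students per term | Two terms | Consent for 220 | Consent for 238 | Three terms | Consent for 220 |
|---|---|---|---|---|---|
| 240 | 480 | 45.8% | 49.6% | 720 | 30.6% |
| 210 | 420 | 52.4% | 56.7% | 630 | 34.9% |
| 180 | 360 | 61.1% | 66.1% | 540 | 40.7% |

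Two terms therefore hold 360/220 = 1.6 to 480/220 = 2.2 times the floor. A third term is needed for 220 only if consent falls below 46% to 61%, and the protocol states no such rate.

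**Step 3: where the shortfall comes from.** It arises from dividing the floor by the term count: 220/3 = 73.3 per term, which is 73.3/240 = 31% consent. Two terms then give 146.7 recruits, or 146.7 × 0.80 = 117.3 tested. At unchanged power the detectable difference would rise from 1.25 to

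- 1.25 × √(176/146.7) = 1.37 points with no drop-out, and
- 1.25 × √(176/117.3) = 1.53 points with 20% drop-out.

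Assuming two-sided alpha 0.05 and ignoring clustering, power for 1.25 points would be 72% and 63% if 80% was planned, or 84% and 75% if 90% was planned. The arithmetic is right, but its starting point is a minimum number of students divided by a minimum number of terms. Neither is an expected value.

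**Step 4: compare that pace with the protocol's other targets.**

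- Data from 460 students over three terms: 460/3 = 153 per term, so 307 in two terms. If 460 means recruits, 307 less 20% to 26% leaves 245 to 227 tested. Both exceed 176.
- The ceiling of 500 over three terms: 500/3 = 167 per term, so 333 in two terms.
- The ceiling of 500 is also close to the whole intake of two terms, 2 × 240 = 480, which suits a plan drawn up for one calendar year.

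A pace of 73 per term is less than half of what the 460 target implies.

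**Step 5: eligibility.** The listed inclusion and exclusion criteria mention no year. The year stands in the line that gives the maximum number of participants. Under Procedures, students consent and are randomised by the end of the lecture week of their own shift, so both arms draw on the same shifts whichever terms are used.

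**The case for a change.** The strongest reply is that the feasibility sentence says three terms are needed, directly after the floor of 220, so the authors evidently expected two terms to fall short. The near-complete uptake in the preliminary study is qualified in the same place as not coming from a randomised trial, so high consent cannot be presumed. The year also stands in the section that defines the population, just above the criteria, and no timeline figure could make both statements literally true.

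Part of this stands. The two statements do conflict, and consent in the trial is unknown. But the sentence joins 220 and three terms with a simple conjunction: it gives no consent rate and does not derive one from the other. Among the three statements (220, three terms, 2022), the term count is the one that the intake figures do not require, so neither the floor nor the year is forced to yield.

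The text also carries dates of different ages. It speaks of a doctors' meeting in March 2021 as still to come, although the version is dated 2023. A year left over from an earlier plan is a more likely explanation than a deliberate restriction that would disqualify a recruited term.

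**Conclusion.** The mismatch is real but clerical. The recruitment period is described as one calendar year in one place and as three terms in two others. Recruiting over either period would be sound: 220 needs 46% to 61% consent over two terms, or 31% to 41% over three. The floor of 220 agrees with 176 tested students at 20% drop-out. The loss of power, with a detectable difference of 1.37 to 1.53 points, holds only under an unstated pace of 73 per term and is not shown to be likely. An ineligible third of the sample is not shown either, because the listed criteria contain no year.

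Naming the terms would tidy the text, but it would leave the sample size, the randomisation, the outcome and the analysis as they are. Analysts would include the consenting, randomised students from whichever terms were run, and the report would give the actual recruitment dates.

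This rests on the protocol's intake figures (180 to 240 students per term) and on consent not falling well below one half. If consent did fall that low, the three-term wording already provides for longer recruitment.

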For the present trial, also the NV students will receive the same non-authentic patient material I.E written theoretical instructions on the MSE, a brief animated movie and some simulated videos by an actor all regarding the MSE. Ensuring it is the authentic patient video e-library and not the theoretical information responsible for the expected difference in scores.

Measures

Baseline measures

The baseline questionnaire, distributed digitally, will entail: Age and gender, unit of clinical rotation, and validated questionnaires on self-regulated learning [36], learning style [37] and on attitude towards psychiatry [38].

Primary outcome – MSE skills test

The test is described in [17]. The test consists of three subtests each consisting of a video vignette, not accessible in the library (i.e. none of the students had seen it previously) with a forced choice test (FCT). After each video, students have five minutes to fill out the MSE template. Each FCT consisted of 20 descriptive one-sentence statements that could be used as part of MSE; the instructions are to mark five, and only five, statements judged to be the most precise description of the case at hand. In each FCT, five statements could correctly be applied to the patient at hand, while five statements are detrimentally wrong. Ten statements are not to the point. We apply a purpose-made scoring algorithm on each FCT: Detrimental false -3 points, not to the point 0 points and correct +3 points. This results in a scoring range of -15 to + 15 points per FCT. The MSE-skills test score consists of the student's average score of the three FCTs. The MSE test will be scheduled at least thrice for each shift, to accommodate for students, who are not able to participate on a particular week-day.

Secondary outcomes

General evaluation of the clinical rotation is carried out by a validated questionnaire of 10 items, to be answered on a 5-point Likert scale [39]. Purpose-made supplementary questions concerning the student's number of patient encounters alone and with a doctor/staff and area of interest in psychiatry is shown in appendix 4. These questions are distributed digitally.

Questions concerning use of the video e-library (time spend on each task/video ; evaluation of/satisfaction with the different element of the e-library will be an intrinsic part of the e-learning program. Time spend and number of visits to the different pages in Absalon will be extracted.

Statistical Analyses

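### The start questionnaire is sent when students learn their arm, with no deadline, so the baseline self-report scales may be answered with knowledge of allocation (minor)

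*Protocol*

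**What the plan says.** Four parts of the Protocol bear on the timing.

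- **Consent and randomisation (Procedures).** Students are approached by email the week before the course, and again after the Monday and Tuesday lectures. Consent runs through the survey system: "electronic signed consent on paper will be gathered by SurveyXact". Then: "Consenting students will be entered in the data management system, and randomized by the end of the lecture week".
- **Disclosure (Procedures; Partial blinding).** "The first day of the clinical rotation participating students will be informed of their allocation". The unblinded secretary "sends emails informing the students of allocation" and also opens access to the library. The same section concedes that "it will not be possible to blind students or local lecturers to allocation group".
- **Survey dispatch (Procedures).** "Questionnaires will be sent by Survey Exact at start and end of the clinical rotation". No day, order or deadline is given.
- **Content (Baseline measures).** "The baseline questionnaire, distributed digitally, will entail: Age and gender, unit of clinical rotation", followed by validated scales on self-regulated learning, learning style and attitude towards psychiatry. This section gives no date.

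Project Content and Activities commits the project to survey data before and after, without tying the first survey to randomisation or disclosure.

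**The concern.** A baseline measure is useful because the arm cannot have affected it. Here the only send time the Protocol gives for a pre-rotation survey falls at about the moment when students learn whether they have the videos.

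A student who answers afterwards may rate attitude or study habits differently because access was granted or refused, and may be more or less inclined to reply at all. The Protocol itself places two of the three constructs near the intervention: it titles the intervention self-regulated training, and under Perspectives it hopes that better training will improve how psychiatry is viewed. Because the allocation email and library access come from the same person, and the survey has no closing date, a late reply from the video arm could even follow the first viewing.

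At stake is whether these scales can serve as a clean description of the groups, as the first half of the before-and-after survey data, or as a covariate or moderator if the analysis plan uses them that way.

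**Working it through.** The Protocol gives no figure to reproduce. The check is one of sequence, followed by a count of what is exposed.

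**Sequence**

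1. Consent: from the week before the course into the lecture week (Procedures).
2. Randomisation: before the lecture week is over (Procedures).
3. Rotation: three weeks, after the lecture week (Non-video group).
4. Disclosure: day 1 of the rotation, by email, with library access opened by the same secretary (Procedures; Partial blinding).
5. Start questionnaire: at the start of the rotation, day and deadline unstated (Procedures).

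Step 5 therefore comes after step 2 and at about the same time as step 4. Coming after step 2 does no harm, since students do not know their arm until step 4. What matters is whether answers arrive before or after step 4. The text allows both, and nothing requires them to arrive before.

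**Link between the two sections.** Baseline measures has no date, and Procedures does not use the word baseline for the start questionnaire. Apart from the consent form, it is the only survey described before or at the start of the rotation. Treating the two as the same is the natural reading, but it is an inference.

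**What is exposed**

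- Baseline items: age, gender, unit, self-regulated learning, learning style, attitude = 6.
- Open to influence by a known arm: the three scales = 3 of 6. Age and gender are fixed, and the faculty office assigns the unit, so the other 3 of 6 are not open to it.
- Stated hypotheses that use the scales: 0 of 2. The first compares test scores between arms. The second relates test scores to videos viewed and time spent.
- Primary outcome: the skills test after the rotation. No skills test at baseline is described, and an unadjusted comparison of arms does not use the scales.
- Secondary outcomes: the scales are not listed there, and the Protocol does not say that they are repeated.
- Send-outs under this schedule: 3 shifts per term × at least 3 terms = at least 9, covering at least 220 recruited students (RCT Feasibility). This is the reach of the schedule. It does not count students who would answer after disclosure.

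**Size of bias.** None can be computed. The Protocol gives no expected shift in the scales, no correlation with the test score and no adjusted model.

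**The case against.** The strongest reply is that this is mostly silence. A questionnaire sent on the morning of day 1, ahead of the allocation email, would comply with the text, and figures 1 and 3, which are not shown, may settle the order. The scales have no stated role in any hypothesis or outcome, the link to the baseline questionnaire is inferred, and the analyses are left to a plan that is not at hand. Two features may also soften any reaction to the arm: the non-video students get the same non-authentic material, and everyone who takes the skills test gets the library before the exam.

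Much of this stands, and it keeps the point minor. It does not remove it. The send time is a trial procedure that the Protocol itself fixes. It fixes it at a poor moment and without a deadline, although an earlier contact through the same survey system already exists.

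A reader might infer more than the Protocol supports:

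- *That sending the survey after randomisation is itself a fault.* It is harmless until disclosure.
- *That the survey necessarily follows the allocation email.* The order is unstated.
- *That the primary result is biased.* The unadjusted comparison does not use these scales.
- *That nothing could be done later.* If completion times are recorded, late answers could be identified and set aside in a sensitivity analysis. That is a partial remedy, because it does not recover what those students would have answered beforehand.
- *That all three scales are equally at risk.* The Protocol gives less reason to expect this for learning style than for attitude or self-regulated learning.

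**Conclusion.** The point holds as a minor one. Followed as written, the Protocol lets unblinded students complete, or skip, three of the six baseline items after learning their arm, and possibly after first using the library. That weakens the scales as a baseline description, as pre-rotation data and as possible covariates. Age, gender, unit, the unadjusted primary comparison and both hypotheses are not affected.

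The conclusion rests on two things: that the start questionnaire is the baseline questionnaire, and that the figures not shown set no earlier deadline. It says that arm-related answering or non-response is left possible. It does not say that either will occur, and it puts no number on them.

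**What to change.** Replace the sentence on questionnaires in Procedures with wording such as:

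> *The baseline questionnaire is sent through SurveyXact as a separate survey after consent, during the lecture week, and its self-report scales close before the allocation email is sent. The end questionnaire is sent at the end of the clinical rotation.*

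Keeping it separate from the consent form avoids burdening the step on which recruitment depends. Completion should not be a condition of randomisation, so that consent remains the only inclusion criterion. Age, gender and unit can be accepted whenever they are returned.

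The change is feasible. SurveyXact is already used for consent, and students who skip the lectures are reachable, since "they will be asked for consent by email, particularly for those not planning to attend the lectures in the first week".

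The cost is one sentence, an earlier send date in each shift (at least 9), and possibly some missing scale data from students who do not reply before the scales close. If the intended order is already survey first and disclosure second, the same sentence records it.
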